12.4.4 Multiplicity Consideration

This is a Phase 2 study to evaluate the safety, tolerability, systemic pharmacokinetics, and pharmacodynamics of AXR-159 Ophthalmic Solution in patients with dry eye disease. There will be no multiplicity adjustments for the multiple treatment groups or multiple primary endpoints.

12.4.5 Primary Efficacy Analyses

The primary efficacy variables (Pre-CAE®) are:

- Change from Baseline to Month 3 in inferior corneal staining score (Ora Calibra® scale) in the study eye
- Change from Baseline to Month 3 in total corneal staining score (Oxford and Ora Calibra® scales) in the study eye
- Change from Baseline to Month 3 in eye dryness measured using a visual analogue scale (VAS)
- Change from Baseline to Month 3 in Total Ocular Surface Disease Index (OSDI) score, and

The primary variables will be summarized as described in [Section 12.4.1](#). The primary efficacy analysis will use the mITT population with LOCF.

Statistical tests will be performed for each AXR-159 Ophthalmic Solution group versus vehicle group at matched dosing frequency (TID or BID). ANCOVA models will be used to compare the change from baseline primary efficacy variables. The ANCOVA models will include terms for baseline value, baseline inferior corneal staining score (ICCS) and baseline eye dryness score as covariates and treatment (AXR-159 or vehicle) as a factor in the model. Pairwise comparisons will be performed for each AXR-159 treatment group versus vehicle using t-tests of the least square means from this model. Two-sided confidence intervals (95%) will be provided for the differences between treatments. As supportive analyses, two-sample t-tests and Wilcoxon rank sum tests will also be conducted.

Details of additional supportive primary efficacy analyses will be provided in the statistical analysis plan.

12.4.6 Secondary Efficacy Analyses

Continuous secondary efficacy variables (see [Section 8.1.2](#)) and changes from baseline in these measures will be summarized as described in [Section 12.4.1](#), and analyzed by visit using ANCOVA as described for the primary efficacy analyses.

Binary clinical cure variables representing clinical cure will be defined by visit for TBUT ≥ 10 , Schirmer's test ≥ 10 mm, Total OSDI < 18 , and Ocular Discomfort Score = 0. These binary variables will be summarized as described in [Section 12.4.1](#). Additionally, within each treatment group, shift tables for complete treatment response (yes/no) in the study eye relative to baseline will be presented for each variable.

The Cochran-Mantel-Haenszel test, stratified by baseline inferior corneal staining score (ICCS, > 1.5 and ≤ 1.5) and eye dryness score (≥ 60 and < 60) will be used to compare treatments with respect to the proportion of cured patients. Pairwise comparisons will be performed for each AXR-159 treatment group versus vehicle. Two-sided confidence intervals (95%) will be provided for the differences between treatments. The confidence intervals will be constructed using the normal approximation to the binomial distribution.

The secondary efficacy analysis will use the mITT population with observed data only.

Details of additional secondary efficacy analyses will be provided in the statistical analysis plan.

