12.1 Sample Size Determination

The sample size is determined empirically. Xiidra achieved a 0.25 unit difference between lifitegrast ophthalmic solution and vehicle in mean change from baseline to day 84 in inferior cornel staining and a standard deviation of approximately 0.75 in Phase 2. Sample sizes for this study are based on detecting a 0.35 unit difference between the active and vehicle groups, assuming a standard deviation of 0.75. In Stage 1 the number of expected enrolled subjects varies between 43 and 53 subjects in the active group and between 37 and 47 subjects in the vehicle group. In Stage 2 the number of expected enrolled subjects is 60 in the active group and 30 to 60 subjects in the vehicle group. Thus, the combined sample provides between 103 and 113 subjects in the active group and between 67 and 77 subjects in the matching vehicle group or between 97 and 107 subjects in the combined vehicle group. Under these assumptions and allowing a dropout rate of 10%, sample sizes of 93 in the active treatment group and 60 in the vehicle group will yield 80% power to show a significant difference at the $\alpha = 0.05$ level using a two-sample t-test.

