12.4 Statistical Analyses

12.4.1 General Approach

In general, continuous data will be summarized with descriptive statistics (number of subjects, mean, standard deviation, median, minimum, and maximum) and will be analyzed using analysis of variance (ANOVA), analysis of covariance (ANCOVA) techniques, two-sample t-tests or Wilcoxon rank sum tests for between-group comparisons, and paired t-tests or sign-rank tests for within-group analyses. Categorical variables will be summarized by number of subjects (n), frequency counts, and percentages, and they will be analyzed using Pearson's chi-square test or Fisher's exact test (if the expected cell count is less than 5 in 25% or more of the cells). Ordinal variables will be analyzed using the Cochran-Mantel-Haenszel (CMH) or the Wilcoxon rank-sum test for between-treatment comparisons and the sign-rank test for within-treatment comparisons.

All summaries will be presented by treatment group and visit. Summaries will be provided for demographics, baseline medical history, concurrent therapies, and subject disposition.

For the purpose of summarization, medical history, concurrent therapies, and adverse events will be coded to MedDRA and WHO Drug dictionaries, as appropriate.

Baseline measures are defined as the last measure prior to the initiation of study treatment, usually at Day 1. If a measure is taken both pre-CAE® and post-CAE®, the baseline will be the last time point matched value prior to the initiation of study treatment. For post-CAE® measures, this will be at Day -14. For changes from pre-CAE® to post-CAE® post first treatment, the change from pre-CAE® to post-CAE® at Day -14 will be considered the baseline value.

Changes from baseline will be calculated as visit – baseline and summarized by treatment and visit as described above. Treatment comparisons between an active treatment and vehicle will be calculated as active – vehicle.

All primary and secondary analyses will be two-sided at a significance level of 0.05. 95% confidence intervals will be provided where appropriate.

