13.2.1 UNANESTHETIZED SCHIRMER'S TEST

Unanesthetized Schirmer's Test will be assessed on both eyes at all visits. Visit 1 and 5 assessments will be pre-CAE®. The Schirmer's test strip will be placed in the lower temporal lid margin of each eye. After 5 minutes, the test strip will be removed and the length of the moistened area will be recorded in millimeters (mm) for each eye. Lower values indicate less tears produced in the eye.

Unanesthetized Schirmer's Test will be summarized by treatment group and visit using quantitative summary statistics. Change from baseline will be also summarized.

Pairwise two-sample t-tests will be employed to compare treatment and vehicle means at each visit and time point. The differences in means, two-sided 95% CIs for the difference in means and p-values will be reported. Wilcoxon rank sum tests will also be conducted. Analyses will be performed on the mITT population with observed data only.

Changes from baseline will be compared between treatment groups using ANCOVA models that adjust for baseline value, baseline inferior corneal staining (Ora Calibra® scale) and baseline eye dryness (VAS). The differences in means, two-sided 95% CIs for the difference in means and p-values will be reported. T-tests and Wilcoxon rank sum tests will also be conducted. Analyses will be performed on the mITT population with observed data only.

Binary clinical cure variables will be defined by visit for Schirmer's test ≥ 5 mm, Schirmer's test ≥ 10 mm and Schirmer's change from baseline ≥ 5 mm, and will summarized by visit using number of subjects, frequency counts and percentages. Treatment groups will be compared pairwise with vehicle using Pearson's chi-square test or Fisher's exact test if the expected cell count is less than 5 in 25% or more of the cells. In addition, the proportion of responders will be compared between treatment groups using the Cochran-Mantel-Haenszel method stratifying by baseline ICSS (≤ 1.5 , > 1.5) and baseline eye dryness (< 60 , ≥ 60). For the Cochran-Mantel-Haenszel analysis of the combined Stage 1 and Stage 2 data, the study Stage will also be included as a stratification factor.

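### The only stated method for cure-difference confidence intervals is the normal approximation, which can under-cover and contradict the adjacent test if cure rates are low; the SAP should name a score-type interval

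*Protocol*

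**What the plan says.** Protocol 12.4.6 defines four binary cure variables by visit: TBUT of at least 10 seconds, Schirmer of at least 10 mm, total OSDI below 18, and an ocular discomfort score of 0. Its provisions for comparing them are:

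- Test: "The Cochran-Mantel-Haenszel test, stratified by baseline inferior corneal staining score" and by eye dryness score, two levels each, so four strata.
- Interval: "Two-sided confidence intervals (95%) will be provided for the differences between treatments", and these are to be "constructed using the normal approximation to the binomial distribution". Whether the interval is stratified is not stated.
- Data: "The secondary efficacy analysis will use the mITT population with observed data only", so dropouts reduce the counts.

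The SAP takes precedence over the protocol's methods (Section 1). For the cure variables (13.2.1, 13.2.2, 13.2.4 to 13.2.7, 13.2.8.1, 13.2.11) it gives Pearson's chi-square, or Fisher's exact test "if the expected cell count is less than 5 in 25% or more of the cells", plus the stratified CMH test, with Stage as a further stratum in combined data. It gives no construction for an interval on a cure difference. Section 8.4 sets only the level (95%, two-sided), and Section 18 declares no departures from the protocol.

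**The concern.** The SAP provides an alternative test for low expected counts but no matching provision for the interval. The only interval rule in either document is the simple normal-approximation (Wald) form, which is known to behave badly when events are few. The Stage 2 arms are not large: "In Stage 2 the number of expected enrolled subjects is 60 in the active group and 30 to 60 subjects in the vehicle group".

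Two things are at stake. A nominal 95% interval may cover less than 95%. It may also disagree with the p-value printed beside it. Because no multiplicity adjustment is made, readers will lean on estimates and intervals, so these should be valid and consistent with the test.

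**Working it through.** **The plan's own figure.** The only power statement (Protocol 12.1) concerns inferior corneal staining: difference 0.35, SD 0.75, 93 versus 60. The standard error is 0.75 × √(1/93 + 1/60) = 0.124, and 0.35/0.124 − 1.96 = 0.86. That gives 80.5% power by the normal approximation and 80.0% with the t distribution, so it reproduces. Nothing comparable is stated for the cure endpoints.

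**Inputs.**
- Arm sizes (Protocol 12.1): Stage 1, 43 to 53 active and 37 to 47 vehicle; Stage 2, 60 active and 30 to 60 vehicle. The 2:2:2:2:1:1:1 ratio gives 330/11 = 30 per unit, hence 60 versus 30. With 10% dropout this is 54 versus 27.
- Cure rates: not documented. I assume a range of 1% to 40%. Pairs below are active/vehicle.

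**Formulas.** Wald: d ± 1.96 × √[p₁(1−p₁)/n₁ + p₂(1−p₂)/n₂], with observed proportions. Newcombe combines the two Wilson limits. Coverage is exact: the sum of binomial probabilities over all outcomes whose interval contains the true difference.

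**Results at 60 versus 30 (unstratified intervals).**

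| True rates | Wald coverage | Newcombe coverage |
|---|---|---|
| 2%/2% | 98.1% | 99.2% |
| 5%/5% | 91.7% | 97.6% |
| 10%/10% | 92.9% | 96.3% |
| 10%/2% | 92.6% | 98.4% |
| 2%/10% | 89.9% | 97.6% |
| 20%/10% | 94.1% | 95.8% |
| 30%/20% | 93.7% | 95.0% |
| 40%/30% | 94.1% | 94.9% |

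Not every low-rate pair is bad: 10%/5% gives Wald 94.7% and 15%/5% gives 95.3%.

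**Other sizes (Wald).**
- 54 versus 27: 92.3% at 5%/5% and 92.6% at 10%/10%.
- 43 versus 37: 88.2% at 2%/10% and 88.6% at 5%/1%, but 95.8% at 5%/5%.
- 93 versus 60: 96.0% at 2%/2%, 94.1% at 5%/5%, 94.5% at 10%/10% and 94.3% at 30%/20%. The lowest found was 92.5%, at 2%/10%.

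**Zero width.** With no cures in either arm the Wald interval is 0 to 0. At 2%/2% this has probability 0.98⁹⁰ = 16.2% (60 versus 30) or 0.98⁸¹ = 19.5% (54 versus 27). At 5%/5% and 60 versus 30 it is 1.0%. For 0/60 versus 0/30 Newcombe gives −11.4 to +6.0 points.

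**A concrete contradiction.** Take 4/60 versus 0/30.
- d = 6.67 points; SE = √(0.0667 × 0.9333/60) = 3.22 points; Wald interval 0.4 to 13.0, excluding zero.
- Expected cures are 4 × 60/90 = 2.7 and 4 × 30/90 = 1.3, so two of four cells are below 5 and the SAP rule selects Fisher's exact test: p = 0.30.

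**Role of stratification.** Simulation at 60 versus 30 with four near-equal strata:
- At 10%/2% the Wald interval excludes zero in 52% of trials and CMH rejects in 16%; they disagree in 36%.
- A stratified normal-approximation interval (Mantel-Haenszel weights, Sato variance) covers 91.8% at 5%/5% and 93.5% at 10%/2%, so stratifying barely helps.
- With prognostic strata (vehicle 30/15/10/2%, active 45/30/20/6%) the unstratified Wald interval covers 95.9%, and it disagrees with CMH in only 3% of trials.

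**The case against.** The strongest reply is that the SAP governs, does not repeat the normal-approximation sentence, and so may have dropped it. That does not remove the point. With no declared change, either the protocol's sentence still applies or the promised interval has no method; both call for the same SAP line.

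Second, low cure rates are assumed. Entry criteria leave room for higher ones: Schirmer entry is 1 to 10 mm against a cure threshold of 10 mm, and OSDI entry is above 18 against a cure below 18. This stands. Low rates are more plausible for discomfort = 0, and for the clearing variables that the SAP adds (redness = 0, staining = 0), but the protocol's interval sentence covers only its own four variables.

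Third, the consequence is small: the endpoints are secondary, SAP 8.5 calls all efficacy analyses exploratory, and no decision rule uses these intervals. This also stands.

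A reader might draw stronger conclusions that the documents do not support:
- That the reported intervals lack 95% coverage in general. This depends on the unknown rates.
- That the interval is documented as unstratified. This is the natural reading, but it is not stated.
- That the Fisher rule shows the plan expects sparse cells. It is a conditional default for all categorical variables (Protocol 12.4.1).

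**Conclusion.** The point holds conditionally, as a minor one. If true cure rates are about 2% to 10%, Wald coverage can fall to about 90% to 93% at 60 versus 30 and to about 88% at 43 versus 37, and the interval can contradict the CMH or Fisher result. At 20% to 40% the loss is about one point. At 93 versus 60, coverage is about 94% to 96% in most cases, with 92.5% the lowest found.

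Two inferences should be resisted. Under-coverage and zero-width intervals are not one combined harm: zero width is frequent near 2% in both arms, where the interval over-covers. Nor does missing stratification cause the under-coverage. The Wald form does, and stratification matters only for coherence with the CMH test.

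The coverage figures assume independent binomial counts and the planned arm sizes. The rates are my assumption.

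**What to change.** State in the SAP that intervals for cure differences use a score-type method (Newcombe or Miettinen-Nurminen), stratified by the CMH factors, with Stage added in combined data, and give a rule for empty or zero-event strata.

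This takes one sentence and no new data. The price is wider intervals when rates are low. At 60 versus 30, unstratified Newcombe is on average about 10% wider than Wald at 10%/10%, about 30% wider at 5%/5% and roughly double at 2%/2%, with essentially no change at 20% to 40%. A stratified Newcombe version (simulated with four equal strata and Mantel-Haenszel weights) costs about the same: mean width 0.245 against 0.180 at 5%/5%, and 0.210 against 0.104 at 2%/2%. Stratified coverage itself was not computed here, so the zero-cell rule should be checked by simulation before it is fixed.

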A patient will be considered a responder if a cure is reached for TFBUT (i.e., ≥ 10 sec), a Schirmer's test (i.e., ≥ 10 mm), Total OSDI (< 18), or Ocular Discomfort Score (Score = 0) at a post-randomization visit. The visit for the primary variable is month 3 and the primary analysis population is mITT with last observation carried forward (LOCF). Statistical tests will be performed for each AXR-159 Ophthalmic Solution group versus vehicle group. Pairwise comparisons of the proportion of responders will be performed using the CMH method stratifying by baseline eye dryness score and baseline inferior corneal staining score. There will be no alpha adjustment for the multiple tests for the pairwise comparisons or multiple endpoints.

An interim analysis will be performed when the last enrolled patient in Stage 1 completes Month 3 of the Expansion Cohort. There is no plan to stop the study for efficacy on the basis of the interim analysis. However, termination of individual dose groups due to safety, tolerability and/or futility may occur. Statistical significance will not be declared at the time of the interim analysis.

A final database lock will occur at the completion of Stage 2 and the safety, tolerability, and efficacy data from both Stage 1 and 2 will be analyzed separately and in a combined fashion to fully leverage the advantage of this two-stage study design. At the final analysis, statistical significance will be declared for two-sided p-values < 0.05 .

Safety: Safety measures will be analyzed using the safety population. Medical Dictionary for Regulatory Activities (MedDRA) nomenclature will be used to code adverse events. Incidence rates of each treatment-emergent adverse event will be summarized by primary system organ class and preferred term. Summary tables will be generated for all treatment-emergent adverse events regardless of causality as well as for those considered to be treatment-related.

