10.2.2 Rescue Medications

In the event that rescue medication is required for worsening signs or symptoms of dry eye disease during the course of the study, patients will be provided an appropriate rescue regimen by the investigator/treating clinician, and will be exited from the study.

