12.4.3 Missing Data

The primary efficacy analyses will be performed using Last Observation Carried Forward (LOCF) methodology. For the LOCF analyses of the primary efficacy variables at Month 3, the last value from the previous visits will be carried forward, matching pre-CAE® or post-CAE® time points. A pre-CAE® time point will never be imputed for a post-CAE® value, and vice versa.

An analysis using observed data only will also be performed for the primary efficacy variables. As additional sensitivity analyses, Markov Chain Monte Carlo (MCMC) multiple imputation methodology may be used to impute missing data for the analyses of the primary efficacy variables.

No secondary efficacy endpoints or safety endpoints will be imputed.

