13.2 Secondary Analyses

The continuous and ordinal secondary efficacy variables collected at each visit will be summarized descriptively (n, mean, SD, median, min and max) by visit and treatment group. Change scores from pre- to post-CAE[®] will be calculated as post-CAE[®] score minus pre-CAE[®] score. Changes from baseline will also be summarized descriptively by visit and treatment group. No imputation will be performed for secondary efficacy variables. Analyses will be performed on the mITT population with observed data only. All secondary measures will also be presented in subject listings.

The following secondary efficacy endpoints will be tested:

- Unanesthetized Schirmer's Test
- TFBUT

- Conjunctival Redness Score
- Fluorescein Corneal Staining (Ora Calibra® scale)
- Fluorescein Corneal Staining (Oxford scale)
- Lissamine Green Conjunctival Staining (Oxford scale)
- Ocular Discomfort Score
- Ocular Discomfort & 4-Symptom Questionnaire
- VAS
- OSDI
- SANDE

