TABLE 14.2.18.3.3	SYMPTOM ASSESSMENT IN DRY EYE (SANDE) STRATIFIED BY TIME TO CAE QUALIFICATION – COMBINED STAGE 1 AND STAGE 2	MITT POPULATION WITH OBSERVED DATA ONLY
TABLE 14.2.19.1.1	RESPONDER ANALYSIS – STAGE 1	MITT POPULATION WITH OBSERVED DATA ONLY
TABLE 14.2.19.1.2	RESPONDER ANALYSIS – STAGE 2	MITT POPULATION WITH OBSERVED DATA ONLY
TABLE 14.2.19.1.3	RESPONDER ANALYSIS – COMBINED STAGE 1 AND STAGE 2	MITT POPULATION WITH OBSERVED DATA ONLY

Table Number	Title	Population
TABLE 14.2.20.1.1	RESPONDER SHIFT FROM BASELINE – STAGE 1	MITT POPULATION WITH OBSERVED DATA ONLY
TABLE 14.2.20.1.2	RESPONDER SHIFT FROM BASELINE – STAGE 2	MITT POPULATION WITH OBSERVED DATA ONLY
TABLE 14.2.20.1.3	RESPONDER SHIFT FROM BASELINE – COMBINED STAGE 1 AND STAGE 2	MITT POPULATION WITH OBSERVED DATA ONLY
TABLE 14.2.21.1.1	P-VALUE SUMMARY – STAGE 1	MITT POPULATION WITH OBSERVED DATA ONLY
TABLE 14.2.21.1.2	P-VALUE SUMMARY – STAGE 2	MITT POPULATION WITH OBSERVED DATA ONLY
TABLE 14.2.21.1.3	P-VALUE SUMMARY – COMBINED STAGE 1 AND STAGE 2	MITT POPULATION WITH OBSERVED DATA ONLY
TABLE 14.3.1.1.1	ADVERSE EVENT SUMMARY – STAGE 1	SAFETY POPULATION
TABLE 14.3.1.1.2	ADVERSE EVENT SUMMARY – STAGE 2	SAFETY POPULATION
TABLE 14.3.1.1.3	ADVERSE EVENT SUMMARY – COMBINED STAGE 1 AND STAGE 2	SAFETY POPULATION
TABLE 14.3.1.2.1	ALL OCULAR ADVERSE EVENTS	SAFETY POPULATION
TABLE 14.3.1.2.2	ALL OCULAR ADVERSE EVENTS – STAGE 2	SAFETY POPULATION
TABLE 14.3.1.2.3	ALL OCULAR ADVERSE EVENTS – COMBINED STAGE 1 AND STAGE 2	SAFETY POPULATION
TABLE 14.3.1.3.1	ALL NON-OCULAR ADVERSE EVENTS – STAGE 1	SAFETY POPULATION
TABLE 14.3.1.3.2	ALL NON-OCULAR ADVERSE EVENTS – STAGE 2	SAFETY POPULATION
TABLE 14.3.1.3.3	ALL NON-OCULAR ADVERSE EVENTS – COMBINED STAGE 1 AND STAGE 2	SAFETY POPULATION
TABLE 14.3.1.4.1	ALL OCULAR TREATMENT-EMERGENT ADVERSE EVENTS – STAGE 1	SAFETY POPULATION
TABLE 14.3.1.4.2	ALL OCULAR TREATMENT-EMERGENT ADVERSE EVENTS – STAGE 2	SAFETY POPULATION
TABLE 14.3.1.4.3	ALL OCULAR TREATMENT-EMERGENT ADVERSE EVENTS – COMBINED STAGE 1 AND STAGE 2	SAFETY POPULATION
TABLE 14.3.1.5.1	ALL NON-OCULAR TREATMENT-EMERGENT ADVERSE EVENTS – STAGE 1	SAFETY POPULATION
TABLE 14.3.1.5.2	ALL NON-OCULAR TREATMENT-EMERGENT ADVERSE EVENTS – STAGE 2	SAFETY POPULATION
TABLE 14.3.1.5.3	ALL NON-OCULAR TREATMENT-EMERGENT ADVERSE EVENTS – COMBINED STAGE 1 AND STAGE 2	SAFETY POPULATION
TABLE 14.3.1.6.1	ALL OCULAR TREATMENT-RELATED TREATMENT-EMERGENT ADVERSE EVENTS – STAGE 1	SAFETY POPULATION

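### Observed-data cure proportions drop patients exited for rescue from later-visit denominators, so the arm contrast depends on who stays in the study

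*Protocol*

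**What the plan says.** Protocol 12.4.6 sets up the cure endpoints: "Binary clinical cure variables representing clinical cure will be defined by visit for TBUT" and, in the same sentence, for Schirmer's test, Total OSDI and Ocular Discomfort Score. It tests them with a stratified CMH test and closes with "The secondary efficacy analysis will use the mITT population with observed data only". Protocol 12.4.3 and SAP 8.2 both say: "No secondary efficacy endpoints or safety endpoints will be imputed". SAP 13.2 repeats it: "No imputation will be performed for secondary efficacy variables. Analyses will be performed on the mITT population with observed data only". The SAP adds further binary variables (redness, fluorescein and lissamine staining, other Schirmer and TFBUT cut-offs) and a chi-square or Fisher test beside CMH. In SAP Section 20, Tables 14.2.19.1.1 to 14.2.19.1.3, ending with "RESPONDER ANALYSIS – COMBINED STAGE 1 AND STAGE 2", carry the mITT observed-data population.

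On rescue for worsening signs or symptoms, Protocol 10.2.2 says that "patients will be provided an appropriate rescue regimen by the investigator/treating clinician, and will be exited from the study". Protocol 7.5 asks sites to try to complete exit procedures at early discontinuation, but no text says which visit those values belong to.

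One statement points the other way. The general methods paragraph of the Protocol synopsis describes the mITT population with LOCF and assigns it to the primary and the secondary efficacy analyses.

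**The concern.** A patient exited for rescue has missing later visits because treatment failed, and the protocol itself creates that missingness. With observed data and no imputation, such a patient is not counted as uncured at Month 3. The patient is simply not counted. The reported proportion is then conditional on remaining in the study, which is a post-randomisation outcome that treatment can change through tolerability on active or lack of effect on vehicle. A by-visit CMH or chi-square test uses nothing from the patient's earlier visits, so it is unbiased only if, within the baseline strata, leaving is unrelated to outcome. Exit for worsening disease contradicts that.

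The stake is how the responder tables are read. SAP Section 20 puts tables labelled Stage 1 into the interim analysis, and Table 14.2.19.1.1 is one of them. Protocol 6.1 has the Data Review Committee look at Stage 1 efficacy before recommending Stage 2, and lets it drop groups judged likely futile. An arm that loses more of its failures would show a flattering cure rate at that point.

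**Working it through.** **The rule.** Protocol 12.4.3 and 12.4.6, SAP 8.2 and 13.2, and the responder table list all agree on observed data. None states the denominator of the cure proportions; it is inferred from observed data plus no imputation. Neither document has a non-responder rule. The LOCF and MCMC analyses are specified for the primary variables, so the responder endpoints have no missing-data sensitivity analysis.

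**The plan's own figure.** The documents give no figure for any responder endpoint. The one power statement (Protocol 12.1, SAP 5) concerns inferior corneal staining: 93 versus 60, difference 0.35, SD 0.75, two-sided 0.05, 80% power. Noncentrality is 0.35/(0.75 × √(1/93 + 1/60)) = 2.82. Power is 80.5% by the normal approximation and 80.0% by noncentral t (df 151), so the figure reproduces. The enrolled sizes behind it are the lower bounds, 103 active and 67 matching vehicle: 103 × 0.9 = 92.7 and 67 × 0.9 = 60.3.

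**Formula.** Let r be the cure proportion with exits counted as non-responders, and e the share of the arm exited before the visit. Assume no exited patient would count as cured. Then the observed-data rate = r/(1 − e). At e = 10%, the plan's all-cause dropout, the inflation factor is 1/0.9 = 1.11 in each arm and equal r gives no false difference.

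**Unequal exits, equal true rates.** Assumed exits are 15% and 5%, either side of the stated 10%.

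| True rate r, both arms | Arm with 15% exits, r/0.85 | Arm with 5% exits, r/0.95 | False difference (points) |
|---|---|---|---|
| 10% | 11.8% | 10.5% | 1.2 |
| 20% | 23.5% | 21.1% | 2.5 |
| 30% | 35.3% | 31.6% | 3.7 |
| 40% | 47.1% | 42.1% | 5.0 |

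If active is the arm with 15% exits and enrolment is 103 versus 67, the chance of a nominally significant result favouring active rises from 2.5% to about 4%, 5%, 7% and 9% in the four rows. For the 30% row, the observed sizes are 103 × 0.85 = 87.55 and 67 × 0.95 = 63.65. The pooled SE is 0.0779, the unpooled SE is 0.0775, and Φ((0.0372 − 1.96 × 0.0779)/0.0775) = 6.8%.

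**Whole-number example.** Take 103 active and 67 vehicle, all in the mITT, with 31 and 20 cured at Month 3. With exits as non-responders: 31/103 = 30.1% and 20/67 = 29.9%, difference +0.2 points whatever the exit pattern. Observed data only:
- exits 10 and 7: 31/93 = 33.3% and 20/60 = 33.3%, difference 0.0;
- exits 15 and 3: 31/88 = 35.2% and 20/64 = 31.3%, difference +4.0;
- exits 5 and 10: 31/98 = 31.6% and 20/57 = 35.1%, difference −3.5.

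**Effect of the alternative rule.** Observed rates of 30% in both arms with exits of 15% active and 5% vehicle become 0.30 × 0.85 = 25.5% and 0.30 × 0.95 = 28.5%, a difference of −3.0 points against an observed 0. Observed rates of 30% active and 20% vehicle with exits of 5% and 15% become 0.30 × 0.95 = 28.5% and 0.20 × 0.85 = 17.0%, a difference of 11.5 points against an observed 10.0.

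**The case against.** The strongest reply is that little depends on these endpoints. They are secondary, SAP 8.5 calls all efficacy analyses exploratory, and the trial is not powered on any cure rate. The primary variables already have LOCF, observed-data and MCMC analyses, and these include Total OSDI, the continuous form of one of the four protocol cure measures. That stands. It limits the weight of the point, but TBUT, Schirmer's test and Ocular Discomfort Score have no such cover.

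The size is also assumed and modest. At 103 versus 67 and 30% cured, the SE of the difference is √(0.21 × (1/103 + 1/67)) = 7.2 points, so a shift of 3.7 is about half an SE. The 10% in the plan is all-cause dropout, and exits for failure may be fewer. SAP Section 9 tabulates discontinuations by arm, so an imbalance would be visible. All of this stands, but seeing an imbalance does not correct the responder table.

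Three stronger readings are tempting, and the documents do not support them.
- A reader might infer that the synopsis ties the responder comparison to LOCF, because "the primary analysis population is mITT with last observation carried forward (LOCF" sits in the paragraph that defines a responder. That sentence is about the primary variable. The actual conflict is the synopsis statement on general methods. The SAP says that it supersedes the protocol's methods, and LOCF would not by rule make a rescued patient a non-responder either.
- A reader might infer that rescued patients vanish altogether. Cure is defined by visit, so they count at each visit attended before exit. Only someone who leaves before any post-baseline assessment is lost from the mITT entirely.
- A reader might infer that counting every discontinuation as failure is the safe, conservative choice. It is not when vehicle patients leave more often: the last example widens the active advantage from 10.0 to 11.5 points. It would also score as treatment failure the administrative exits, losses to follow-up and sponsor terminations listed in Protocol 10.6.2.

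**Conclusion.** The point holds as a narrow one. Followed as written, the plan removes patients exited for rescue from the cure denominators at later visits, and no rule or sensitivity analysis puts them back. Under equal true rates of 10% to 40% and assumed exits of 15% versus 5%, the false difference is about 1 to 5 points in favour of the arm with more exits. With equal exits and equal true rates it is zero. The direction cannot be known in advance. These figures rest on assumed exit shares and cure rates, on exited patients being uncured, and on the inferred denominator. The consequence is for the interpretation of exploratory secondary endpoints, including the Stage 1 responder table at the interim analysis. A reader might extend it to the primary analysis, but the observed-data rule at issue applies to the secondary variables and the primary analysis uses LOCF. The change is worth making because it is cheap and removes a selection tied to treatment failure.

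**What to change.** In SAP 13.2, for all binary cure and responder variables, count mITT patients who exited for rescue, lack of efficacy or an adverse event as non-responders at every later scheduled visit, in both the CMH and the chi-square or Fisher analyses. Keep observed cases as one sensitivity analysis, and add a second that counts all discontinuations as non-responders. State that values from early-exit procedures (Protocol 7.5) do not override this rule at Month 3. Reconcile the synopsis statement on LOCF for secondary analyses with Protocol 12.4.3 and 12.4.6, and record the change in SAP Section 18. The rescue provision itself is untouched; only the analysis changes.

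The cost is one SAP rule and no new assessments. The result will depend on the recorded exit reason. The reasons listed in Protocol 10.6.2 and SAP Section 9 have no separate entry for rescue or lack of efficacy, so these exits should be classified before unmasking, for example from the concurrent-medication record, which under Protocol 10.2 includes the reason for use. The rule is not conservative when vehicle patients exit more often, so both sensitivity analyses should be reported beside it. A patient with no post-baseline assessment remains outside the mITT and is not recovered.
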